The RP2D of nanatinostat in Phase 1b will be defined as the highest dose administered with standard daily doses of valganciclovir (900 mg once or 450 mg twice daily) for which <33% of patients experience a DLT (defined in Section 5.5.3) during the first treatment cycle (28 days) up to a maximum daily dose of 80 mg administered with food either as a single daily dose administered intermittently (Days 1 to 4 per week) or as a split dose twice daily administered continuously (Days 1 to 7 per week). In addition to toxicity, PK, antitumor activity, plus pharmacodynamic markers of disease response (plasma EBV DNA levels) will be considered in the final determination of the RP2D in consultation with the SMC. Dose escalation rules during Phase 1b are presented in Table 5.

Table 5: Phase 1b Dose Escalation Rules for Nanatinostat in Combination with Valganciclovir*

Dose level	Outcome	Action		
-1 Nanatinostat 10 mg daily,	If none of the first 3 patients experiences a DLT	Proceed to expansion cohorts.		
Days 1-4/wk	If 1 of 3 patients experiences a DLT	Enroll 3 more patients into dose level -1		
Valganciclovir 900 mg daily	If 1 of 6 patients experiences a DLT	Declare dose level -1 to be RP2D		
	If ≥2/6 patients experience a DLT	Convene safety review to discuss next steps.		
1 Starting dose	If none of the first 3 patients experiences a DLT	Proceed to dose level 2		
Nanatinostat 20 mg daily,	If 1 of 3 patients experiences a DLT	Enroll 3 more patients into dose level 1		
Days 1-4/wk	If 1 of 6 patients experiences a DLT	Proceed to dose level 2		
Valganciclovir 900 mg daily	If ≥2/6 patients experience a DLT	Decrease nanatinostat to dose level -1 and proceed.		
Nanatinostat 30 mg daily,	If none of the first 3 patients experiences a DLT	Proceed to dose level 3		
Days 1-4/wk	If 1 of 3 patients experiences a DLT	Enroll 3 more patients into dose level 2.		
Valganciclovir 900 mg daily	If 1 of 6 patients experiences a DLT	Proceed to dose level 3.		
	If ≥2/6 patients experience a DLT	Declare dose level 1 the RP2D.		

a: Dose levels 9, 11, and 13 are planned dose levels, while dose levels 8, 10, and 12 are planned provisional dose levels for stepping up or down based on the DLT profile to potentially better determine the RP2D. See Table 5 for further details.

Dose level	Outcome	Action			
3 Nanatinostat 40 mg daily,	If none of the first 3 patients experiences a DLT	Proceed to dose level 6.			

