Days 1-4/wk	If 1 of 3 patients experiences a DLT	Enroll 3 more patients into dose level 3.			
Valganciclovir 900 mg daily	If 1 of 6 patients experiences a DLT	Proceed to dose level 6.			
· · · · · · · · · · · · · · · · · · ·	If ≥2/6 patients experience a DLT	Proceed to dose level 4.			
4 Nanatinostat 20 mg + 10 mg	If none of the first 3 patients experiences a DLT	Declare 30 mg nanatinostat the RP2D*			
divided dose, Days 1-4/wk	If 1 of 3 patients experiences a DLT	Enroll 3 more patients into dose level 4.			
Valganciclovir 900 mg daily	If 1 of 6 patients experiences a DLT	Declare 30 mg nanatinostat the RP2D*			
waganere vir you ing unity	If ≥2/6 patients experience a DLT	Declare dose level 2 the RP2D.			
5 Nanatinostat 20 mg BID,	If none of the first 3 patients experiences a DLT	Declare 40 mg nanatinostat the RP2D*			
Days 1-4/wk	If 1 of 3 patients experiences a DLT	Enroll 3 more patients into dose level 5.			
Valganciclovir 900 mg daily	If 1 of 6 patients experiences a DLT	Declare 40 mg nanatinostat the RP2D*			
	If ≥2/6 patients experience a DLT	Declare dose level 3 the RP2D.			
6 Nanatinostat 10 mg BID,	If none of the first 3 patients experiences a DLT	Proceed to dose level 7.			
Days 1-4/wk	If 1 of 3 patients experiences a DLT	Enroll 3 more patients into dose level 6.			
Valganciclovir 900 mg BID for	If 1 of 6 patients experiences a DLT	Proceed to dose level 7.			
21 days, then daily	If ≥2/6 patients experience a DLT	Proceed to dose level 5.			
7 Nanatinostat 20 mg + 10 mg	If none of the first 3 patients experiences a DLT	Proceed to dose level 9.			
divided dose, Days 1-4/wk	If 1 of 3 patients experiences a DLT	Enroll 3 more patients into dose level 7.			
Valganciclovir 900 mg BID for 21 days, then daily	If 1 of 6 patients experiences a DLT	Proceed to dose level 8 if it has not been previously enrolled, otherwise declare dose level 7 the RP2D.			
	If ≥2/6 patients experience a DLT	Step down to dose level 6 and enroll a total of 6 patients there. Alternatively, declare dose level 6 the RP2D if it has already enrolled 6 patients.			
8 Nanatinostat 20 mg + 10 mg divided dose, Days 1-7/wk	If none of the first 3 patients experiences a DLT	Proceed to dose level 9 if it has not been previously enrolled, otherwise declare dose level 8 the RP2D and expand dose level 8 to 6 patients to confirm RP2D determination.			
Valganciclovir 450 mg twice	If 1 of 3 patients experiences a DLT	Enroll 3 more patients into dose level 8.			

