daily	If 1 of 6 patients experiences a DLT	Proceed to dose level 9 if it has not been previously enrolled, otherwise declare dose level 8 the RP2D.			
	If ≥2 patients experience a DLT	Step down to dose level 7 and enroll a total of 6 patients there. Alternatively, declare dose level 7 the RP2D if it has already enrolled 6 patients.			
9 Nanatinostat 20 mg + 20 mg	If none of the first 3 patients experiences a DLT	Proceed to dose level 11.			
divided dose, Days 1-7/wk	If 1 of 3 patients experiences a DLT	Enroll 3 more patients into dose level 9.			
Valganciclovir 450 mg twice daily	If 1 of 6 patients experiences a DLT	Proceed to dose level 10 if it has not been previously enrolled, otherwise declare dose level 9 the RP2D.			
	If ≥2 patients experience a DLT	Step down to dose level 8 and enroll a total of 6 patients there. Alternatively, declare dose level 8 the RP2D if it has already enrolled 6 patients.			
Nanatinostat 30 mg + 20 mg divided dose, Days 1-7/wk	If none of the first 3 patients experiences a DLT	Proceed to dose level 11 if it has not been previously enrolled, otherwise declare dose level 10 the RP2D and expand dose level 10 to 6 patients to confirm RP2D determination.			

Dose level	Outcome	Action			
Valganciclovir 450 mg twice	If 1 of 3 patients experiences a DLT	Enroll 3 more patients into dose level 10.			
daily	If 1 of 6 patients experiences a DLT	Proceed to dose level 11 if it has not been previously enrolled, otherwise declare dose level 10 the RP2D.			
	If ≥2 patients experience a DLT	Step down to dose level 9 and enroll a total of 6 patients there. Alternatively, declare dose level 9 the RP2D if it has already enrolled 6 patients.			
11 Nanatinostat 30 mg + 30 mg	If none of the first 3 patients experiences a DLT	Proceed to dose level 13.			
divided dose, Days 1-7/wk	If 1 of 3 patients experiences a DLT	Enroll 3 more patients in dose level 11			
Valganciclovir 450 mg twice daily	If 1 of 6 patients experiences a DLT	Proceed to dose level 12 if it has not been previously enrolled, otherwise declare dose level 11 the RP2D.			
	If ≥2 patients experience a DLT	Step down to dose level 10 and enroll a total of 6 patients there. Alternatively declare dose level 10 the RP2D if it has already enrolled 6 patients.			

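### Protocol Table 5: after a step-down from a failed level 7, the level 6 row for 1 DLT in 6 sends the trial back to level 7

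*Protocol*

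**What the plan says.** The rules are in Protocol Table 5 (section 5.5.2).

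- **Level 6, none of the first 3 with a DLT:** "Proceed to dose level 7".
- **Level 6, 1 of 6:** the same instruction, again without a condition.
- **Level 7, 2 or more of 6:** "Step down to dose level 6 and enroll a total of 6 patients there". The alternative is "Alternatively, declare dose level 6 the RP2D if it has already enrolled 6 patients".
- **Level 7, 1 of 6:** "Proceed to dose level 8 if it has not been previously enrolled, otherwise declare dose level 7 the RP2D". The 1-of-6 rows of levels 8 to 12 have the same form.
- **Zero-DLT rows:** those of levels 8, 10 and 12 carry the condition. Those of levels 7, 9 and 11 do not; they read "Proceed to dose level 9", "Proceed to dose level 11" and "Proceed to dose level 13".

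Section 5.5.2 defines the RP2D as the highest nanatinostat dose, given with valganciclovir 900 mg once daily or 450 mg twice daily, "for which <33% of patients experience a DLT" in the first cycle. Table 4 gives levels 6 and 7 valganciclovir 900 mg twice daily for 21 days, which that definition does not cover. The Table 5 footnote says that RP2D in the table means a maximum tolerated or maximum administered dose.

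**The concern.** Level 6 is a step-down target, so its rows have to work on a second pass, when level 7 has already been tried. The 1-of-6 row is worded for a first pass only. Followed literally after a step-down, it directs new patients to a dose that has just had 2 or more DLTs, and no level 6 row says to stop and declare level 6.

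The order of events also changes the instruction. If level 6 reaches 1 of 6 before level 7 opens and level 7 then fails, the table declares level 6. If level 6 reaches 1 of 6 only after level 7 has failed, the table says to escalate. The final counts are the same, but the actions differ.

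**Working it through.** **Trace of the rows**

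| Step | Result | Table 5 action |
|---|---|---|
| 1 | Level 6: 0 of 3 | go to level 7 |
| 2 | Level 7: 2 or more DLTs; level 6 has 3 patients | return to level 6 and fill it to 6 |
| 3a | Level 6: 2 or more of 6 | go to level 5; works as written |
| 3b | Level 6: 1 of 6 | go to level 7, which has failed |
| 3c | Level 6: 0 of 6 | no row names this count; if read into the zero-DLT row, go to level 7, which has failed |

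At levels 7, 9 and 11, 1 of 6 after a step-down is resolved by the condition and the level is declared. Only 0 of 6 is open there:

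- **Level 7.** The path is level 7 at 0 of 3, level 9 fails, level 8 fails, level 7 filled to 0 of 6. The zero-DLT row points to level 9, which has failed. The section 5.5.2 definition does not decide this, because of the level 7 valganciclovir dose.
- **Levels 9 and 11.** Their valganciclovir dose is 450 mg twice daily, so the definition applies: 0/6 = 0% passes, and a higher level with 2/6 = 33.3% or more does not. The current level is the answer.

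**How often the level 6 row is reached**

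The plan states no figure to reproduce and gives no DLT rates for these levels, so the rates below are assumptions. The start is level 6, because Protocol 1.5.3.1 reports no DLTs to date at 40 mg on Days 1 to 4, which I read as level 3 cleared.

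With DLT rate p at level 6 and r at level 7, the direct path 6, 7, 6 has probability

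(1−p)³ × F(r) × 3p(1−p)²,

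where F(r) = P(2 or more of 3) + P(1 of 3) × P(1 or more of the next 3).

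Same rate at both levels:

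| Rate | (1−p)³ | F | 3p(1−p)² | Direct path | Full enumeration |
|---|---|---|---|---|---|
| 5% | 0.8574 | 0.0266 | 0.1354 | 0.0031 | 0.31% |
| 10% | 0.7290 | 0.0939 | 0.2430 | 0.0166 | 1.67% |
| 20% | 0.5120 | 0.2914 | 0.3840 | 0.0573 | 5.84% |
| 30% | 0.3430 | 0.5057 | 0.4410 | 0.0765 | 7.99% |

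The enumeration follows Table 5 from level 6 with the same rate at every level, no over-enrollment or replacements, and step-down levels filled to 6. It adds later returns to level 6, so it slightly exceeds the direct path. Under a common rate the share is close to its maximum near 30% (7.95% at 33%, 6.84% at 40%).

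Level 7 gives more nanatinostat than level 6 (20 mg + 10 mg against 10 mg twice daily), so a higher rate at level 7 is plausible. Direct path only:

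| p | r | Direct path |
|---|---|---|
| 5% | 15% | 0.8574 × 0.1862 × 0.1354 = 0.022 |
| 10% | 25% | 0.7290 × 0.4001 × 0.2430 = 0.071 |
| 20% | 40% | 0.5120 × 0.6907 × 0.3840 = 0.136 |
| 25% | 50% | 0.4219 × 0.8281 × 0.4219 = 0.147 |

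For 0 of 6 after a step-down, at common rates of 5, 10, 20 and 30%, the enumeration gives 1.95, 5.00, 7.78 and 6.22% at level 6, and 0.06, 0.52, 1.90 and 1.78% at level 7.

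All of these are shares of trials that reach a row, not shares of patients treated again at a failed dose.

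**The case against.** The best reply is that nobody would follow the row. The protocol calls Phase 1b a traditional 3+3 design, in which a level with 2 or more DLTs in up to 6 patients is closed. The level 6 row for 1 of 6 reads naturally as the first-pass continuation of 1 of 3. Section 5.5.1 has dose levels settled in discussion with Investigators, and the SMC is consulted on the RP2D. This stands as an argument for low risk. It does not supply the missing rule: it relies on judgment to override a written row.

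A reader might infer that the level 6 row contradicts the level 7 clause "Alternatively, declare dose level 6 the RP2D if it has already enrolled 6 patients". The text does not support that. The clause is an alternative tested when level 7 fails, and on this path level 6 then has only 3 patients, so the other branch applies. What is missing is a correct instruction after level 6 has been filled.

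A reader might also infer that 0 of 6 after a step-down has no row at levels 6, 7, 9 and 11 in particular. The zero-DLT rows of levels 8, 10 and 12 use the same first-3 trigger, so a strict reading leaves those levels open too. On a looser reading 0 of 6 falls into the zero-DLT row everywhere, and only levels 6 and 7 then lack an answer from the row or from section 5.5.2.

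**Conclusion.** The level 6 row for 1 of 6 is wrong as written when it is reached after level 7 has failed. The zero-DLT rows of levels 6 and 7 have the same fault if 0 of 6 is read into them. Levels 9 and 11 are settled by section 5.5.2.

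Under an assumed common DLT rate of 5% to 30%, about 0.3% to 8% of trials starting at level 6 would meet the 1-of-6 row. The upper figure is not a bound: with level 7 more toxic than level 6, the direct path alone reaches about 15% in the pairs tried.

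The consequence for this trial is small. SAP 4.8 reports that enrollment stopped after the final Phase 1b dose level was completed, that an RP2D was determined, and that Phase 2 did not open. A reader might infer that patients were sent back to a failed dose; the documents do not show that this path occurred. The correction matters mainly if Table 5 is used again.

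**What to change.** - **Level 6, 1 of 6:** go to level 7 only if it has not yet been opened; if it has, declare level 6 the RP2D. State that this is RP2D in the maximum-tolerated-dose sense of the Table 5 footnote, because the level 6 valganciclovir dose lies outside the section 5.5.2 definition.
- **Level 6, zero DLTs:** add the same condition.
- **Level 7, zero DLTs:** go to level 9 only if it has not yet been opened; if it has, declare level 7, in the same sense.
- **One note to the table:** at every level, 0 of 6 after a step-down is handled like 1 of 6.

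The cost is wording in three rows and one new note. The condition already exists in the neighboring rows; the note is new text. No patients, visits or procedures are added.

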5.5.3. Dose-Limiting Toxicities (DLTs)

A DLT is defined as an AE or clinically significant abnormal laboratory value that is **at least possibly related** to study drugs and is not primarily related to disease, disease progression, concomitant medication(s), or intercurrent illness. DLTs will be assessed for each phase of the study and will include events that meet any of the criteria outlined in Section 5.5.3.1, Section 5.5.3.2, and Section 5.5.3.3. National Cancer Institute (NCI) Common Terminology Criteria for

Adverse Events (CTCAE) version 5.0 (v5.0) will be used for all AE grading for the purpose of dose-escalation decisions.

5.5.3.1. Phase 1b: Nanatinostat and Valganciclovir

The DLT evaluation period is 28 days.

To be considered a DLT, an AE must meet one or more of the following criteria:

- 1. Hematologic DLTs:
 - Grade 4 neutropenia or thrombocytopenia lasting ≥7 days.
 - Grade ≥3 thrombocytopenia associated with clinically significant bleeding.
- 2. Non-hematologic DLTs:
 - Grade ≥ 3 non-laboratory toxicities despite maximum supportive therapy.
 - Grade ≥3 clinically significant laboratory abnormality for which the patient is symptomatic regardless of its duration, requires medical intervention, is not corrected within 72 hours, or leads to hospitalization.
- 3. Febrile neutropenia, defined as ANC $<1000/\text{mm}^3$ with a single temperature of >38.3 °C (101 °F) or a sustained temperature of ≥ 38 °C (100.4 °F) for more than 1 hour.
- 4. Any treatment-related toxicity that results in a dose hold of >7 consecutive days or causes the patient to discontinue treatment.
- 5. Any Grade 5 toxicity not clearly due to the underlying disease or extraneous causes
- 6. Any Hy's law case: ALT and/or AST >3 × ULN and total bilirubin >2 × ULN not explained by other causes.

5.5.3.2. Phase 2: Nanatinostat and Valganciclovir With or Without Pembrolizumab

The DLT evaluation period is 7 weeks.

Phase 2 of the study will initially have a dose optimization cohort period to assess the safety of the RP2D and '<RP2D' of nanatinostat and valganciclovir determined by the SMC's review of the totality of the data from the previous Phase 1b cohorts. The dose optimization cohort period will be monitored by the study's SMC composed of the lead study Investigators and the Sponsor's Medical Monitor. The evaluation period will be 2 cycles post-initial study drug administration (7 weeks). When all patients enrolled in the dose optimization cohort have completed 2 cycles (7 weeks) of treatment (or discontinued earlier) recruitment will be paused until a safety data review is performed in the following situations:

- 1. If treatment was postponed due to the reasons listed below for more than 2 of the first 6 enrolled patients who received at least one dose of any study drug.
- 2. If treatment was postponed due to the reasons listed below for 4 or more of the first 9 patients who have received at least one dose of any study drug.

The SMC will review the clinical and laboratory data for any DLTs and/or emerging new or unexpected toxicities associated with the nanatinostat and valganciclovir dose to determine the next steps for dosing and continued enrollment.

Following review of the data from the dose optimization cohorts and confirmation of the RP2D, enrollment into the Phase 2 dose expansion will begin, supported by an early safety analysis of the first 6 patients randomized to receive nanatinostat and valganciclovir with pembrolizumab as described in Section 5.5.3.3. Any DLTs and/or emerging new or unexpected toxicities associated with nanatinostat in combination with valganciclovir and pembrolizumab will be evaluated by the SMC who will determine the next steps for dosing and continued enrollment.

To be considered a DLT, an AE must meet one of the following criteria, where the relationship to study drug(s) cannot be ruled out, and the AE is not primarily related to disease, disease progression, concomitant medication(s) or intercurrent illness:

- 1. Hematologic DLTs:
 - Grade 4 neutropenia or thrombocytopenia lasting ≥7 days.
 - Grade ≥3 thrombocytopenia associated with clinically significant bleeding.
- 2. Non-hematologic DLTs:
 - a. Grade ≥ 3 non-laboratory toxicities despite maximum supportive therapy.
 - b. Grade ≥3 clinically significant laboratory abnormality for which the patient is symptomatic regardless of its duration, requires medical intervention, is not corrected within 72 hours, or leads to hospitalization.
- 3. Febrile neutropenia defined as ANC <1000/mm³ with a single temperature of >38.3°C (101°F) or a sustained temperature of ≥38°C (100.4°F) for more than 1 hour.
- 4. Any treatment-related toxicity that causes the participant to discontinue treatment.
- 5. Any Grade 5 toxicity not clearly due to the underlying disease or extraneous causes.
- 6. Any Hy's law case: ALT and/or AST >3 × ULN and total bilirubin >2 × ULN not explained by other causes.

After the nanatinostat and valganciclovir RP2D is confirmed by the SMC based on the results of the dose optimization cohorts, the study will proceed to the Phase 2 dose expansion period. Up to 60 patients with RM-NPC will be randomly assigned 1:1 to receive that RP2D of nanatinostat and valganciclovir with or without concomitant pembrolizumab 200 mg IV every 3 weeks to assess the preliminary antitumor activity, safety, and tolerability of each regimen.

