3. STUDY DESIGN

3.1. Description of Study Design

This is a Phase 1b/2, open-label, multicenter study designed to evaluate the safety and preliminary efficacy of oral nanatinostat and valganciclovir alone and in combination with IV pembrolizumab in patients with EBV⁺ RM-NPC (Figure 3).

Phase 1b:

A traditional 3+3 dose escalation design will be used to determine the RP2D of nanatinostat and valganciclovir; approximately 27 to 60 patients with RM-NPC will be enrolled; cohorts of 3 to 6 patients with RM-NPC will be enrolled sequentially at escalating nanatinostat doses starting with a 20 mg once daily dose on Days 1 to 4 per week (intermittent dosing) with valganciclovir 900 mg daily. Any patients in screening when the last patient is enrolled in a cohort may also be enrolled if eligible. Dose escalation will continue with i) a total daily nanatinostat dose of 30 and 40 mg daily administered as a single dose on Days 1 to 4 per week with valganciclovir 900 mg once daily, ii) as a divided nanatinostat dose twice daily on Days 1 to 4 per week with valganciclovir 900 mg once daily or valganciclovir 900 mg twice daily for 21 days followed by a subsequent dose reduction to 900 mg once daily, or iii) as a split daily dose of nanatinostat starting at 20 mg with valganciclovir 450 mg twice daily, 4 hours apart on Days 1 to 7 per week until the RP2D is determined. Because plasma EBV DNA levels correlate closely with the presence of disease and response to therapy in RM-NPC, these data will be considered together with safety data in the selection of the RP2D.

Phase 2:

Following dose escalation, Phase 2 will begin with a dose optimization cohort to assess the safety, tolerability, PK, pharmacodynamics, and antitumor activity of nanatinostat and valganciclovir and to confirm its RP2D in patients with RM-NPC.

Patients will be randomly assigned 1:1 to each treatment group (up to 20 patients in each treatment group for approximately 40 patients total) during the dose optimization cohort period. The starting doses of nanatinostat for the treatment groups will be the RP2D and another dose level below the RP2D (<RP2D) plus valganciclovir 450 mg twice daily, based on the Safety Monitoring Committee's (SMC's) review of the totality of the data from the previous Phase 1b cohorts.

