After the nanatinostat and valganciclovir RP2D is confirmed by the SMC based on the results of the dose optimization cohorts, up to 60 patients with RM-NPC will be randomly assigned 1:1 to receive that RP2D of nanatinostat and valganciclovir with or without concomitant pembrolizumab to assess the preliminary antitumor activity, safety, and tolerability of each regimen in the Phase 2 dose expansion period. Randomization will be stratified by prior anti-PD-1 treatment exposure.

Pembrolizumab will be dosed at 200 mg IV every 3 weeks for those patients randomly assigned to the nanatinostat, valganciclovir, and pembrolizumab group.

[figure not shown]
An early safety analysis will be performed after the first 6 patients are randomized to receive nanatinostat and valganciclovir in combination with pembrolizumab and have been followed for at least 2 cycles (7 weeks) of treatment as described in Section 5.5.3.3.

In addition, up to 10 patients with advanced EBV⁺ non-NPC solid tumors (gastric cancer, LELC, and leiomyosarcoma) will be enrolled in a Phase 1b exploratory proof-of-concept cohort to characterize the safety and PK of the nanatinostat and valganciclovir combination in other solid tumors. Enrollment in this proof-of-concept cohort will begin when the appropriate RP2D for this population is determined in consultation with the SMC, while enrollment in the proof-of-concept cohort may be stopped before 10 patients are treated if a) evidence of safety or tolerability issues arise or b) Phase 2 of the study completes enrollment.

All patients will be monitored at weekly intervals for the first 6 weeks, and then at 3-week intervals thereafter starting at Week 8. Tumor responses will be assessed at Week 8 and then every 6 weeks for the first 26 weeks (6 months) and every 12 weeks thereafter by the Investigator per Response Evaluation Criteria in Solid Tumors (RECIST) version 1.1 (v1.1). A scan to confirm an unconfirmed PR or unconfirmed CR ≥4 weeks later may also be performed.

Patients will continue to receive study treatment until the development of progressive disease (per Investigator assessment), unacceptable toxicity, withdrawal of consent, Investigator's discretion, initiation of new antineoplastic therapy, or study termination by the Sponsor. The maximum treatment duration with pembrolizumab is 24 months.

Figure 3: Study Design

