5.5.3.3. Assessment of Toxicity During Phase 2 Dose Expansion

Sequential boundaries will be used to monitor the DLT rate during Phase 2 dose expansion (Ivanova 2005). The accrual will be halted if excessive numbers of DLTs (boundary) as defined in Section 5.5.3.2 are seen per arm, and the SMC will have the option of either discontinuing accrual in that arm or reducing the RP2D to reduce the level of toxicity. The boundaries at which accrual is halted or the RP2D is reduced are listed in Table 6. This is a Pocock-type stopping boundary that yields the probability of crossing the boundary at most 5% when the rate of dose-limiting toxicity is equal to the acceptable rate of 30%.

Table 6: Early Stopping Boundaries for Toxicity

Number of Patients	1	2	3	4	5	6	7	8	9	10	11	12	13	14	15
Boundary	-	-	-	4	5	5	6	6	7	7	8	8	9	9	9
Number of Patients	16	17	18	19	20	21	22	23	24	25	26	27	28	29	30
Boundary	10	10	11	11	12	12	12	13	13	14	14	14	15	15	15

An early safety analysis of the first 6 patients randomized to receive nanatinostat and valganciclovir with pembrolizumab will be performed, and a more conservative early stopping boundary than is shown in Table 6 above will be applied if appropriate. If at least two of these patients experience DLTs during their first 2 cycles (7 weeks) of treatment, then patient accrual will be halted, and the SMC will have the option of either discontinuing accrual in that arm or reducing the RP2D to reduce the level of toxicity.

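### As worded, the dose-optimization pause rule on the first 6 and first 9 patients is applied only after the whole cohort has finished 7 weeks, when no cohort recruitment is left to pause

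*Protocol*

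**What the plan says.** Protocol Section 3.1 sets the dose-optimization cohort at "up to 20 patients in each treatment group for approximately 40 patients total", randomized 1:1 to the RP2D and a lower dose. Section 5.5.3.2 gives it a 7-week evaluation period, monitored by the Safety Monitoring Committee (SMC). The pause rule follows: "When all patients enrolled in the dose optimization cohort have completed 2 cycles (7 weeks) of treatment (or discontinued earlier) recruitment will be paused". The pause lasts while safety data are reviewed, and it applies in either of two situations. The first is "If treatment was postponed due to the reasons listed below for more than 2 of the first 6 enrolled patients"; only patients given at least one dose count. The second is the same event in 4 or more of the first 9 treated patients. The SMC then reviews the data "to determine the next steps for dosing and continued enrollment".

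The Phase 2 DLT criteria come later in the same section. They include "Any treatment-related toxicity that causes the participant to discontinue treatment" and "Any Grade 5 toxicity not clearly due to the underlying disease or extraneous causes".

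The expansion period has its own rule. Section 3.1 states its timing: "An early safety analysis will be performed after the first 6 patients are randomized to receive nanatinostat and valganciclovir in combination with pembrolizumab". Those 6 must also have at least 2 cycles of follow-up. Section 5.5.3.3 states what is counted and what happens: "If at least two of these patients experience DLTs during their first 2 cycles (7 weeks) of treatment, then patient accrual will be halted".

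The SAP does not restate the dose-optimization rule. SAP Section 4.8 records that the study stopped before Phase 2.

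**The concern.** A rule on the first 6 and first 9 patients is useful because it can act while most of the cohort is still to be enrolled. Here both triggers depend on the whole enrolled cohort having finished 7 weeks. By then every patient the rule could have spared from a poorly tolerated dose has already been treated. The pause cannot usefully refer to expansion either: Sections 3.4.1.2 and 5.5.3.2 already make expansion wait for review of this cohort's data, whether or not a trigger is met.

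This is the only rule for this cohort that depends on the proportion of patients with toxicity. The Table 6 boundary and the first-6 rule in Section 5.5.3.3 are limited to expansion. Section 5.6.1 acts on death, Grade 4 QTc prolongation, and Grade 4 renal or multi-organ failure in at least 2 patients. A run of prolonged Grade 4 neutropenia, for example, would not trip it.

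**Working it through.** **Timing.** There are three ways to read the condition:
- *All of the roughly 40 patients.* The cohort is full, so there is nothing to pause.
- *The pause means expansion.* It adds nothing, because expansion already waits for the review.
- *All patients enrolled so far.* Under continuous accrual each new patient restarts the 7-week wait, so the moment keeps moving. It arrives only after 7 weeks with no enrollment.

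None of these gives a working early check.

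**Counted event.** The reasons said to be listed below have no list of their own. The Phase 2 DLT criteria are the only numbered criteria that follow, so they are a workable referent. The fit is imperfect. Section 5.5.3.1 (Phase 1b, criterion 4) counts a toxicity-related dose hold of more than 7 consecutive days as well as discontinuation. Phase 2 criterion 4 keeps only discontinuation. The Phase 2 list therefore names no delay, although the rule counts postponements.

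**Pause probability.** The plan states no operating characteristic for this rule. The nearest stated figure is for Table 6, at most 5% at a 30% DLT rate. An exact binomial recursion over that table gives 4.94%, which agrees, but Table 6 covers expansion only.

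For one sequence of patients with true event rate p, let X be the events in the first 6 and Y the events in the next 3. The rule fires with probability

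P(X ≥ 3) + P(X = 2)·P(Y ≥ 2) + P(X = 1)·P(Y = 3).

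At p = 0.30: 0.2557 + 0.3241 × 0.2160 + 0.3025 × 0.0270 = 0.2557 + 0.0700 + 0.0082 = 0.3339.

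| True event rate | At least 3 of 6 | Added at 9 | Total |
|---|---|---|---|
| 10% | 1.6% | 0.3% | 1.9% |
| 20% | 9.9% | 2.9% | 12.8% |
| 30% | 25.6% | 7.8% | 33.4% |
| 40% | 45.6% | 12.1% | 57.7% |
| 50% | 65.6% | 12.9% | 78.5% |

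These totals do not depend on when the counts are read. Timing changes only how many patients have been exposed by then.

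**Patients not yet enrolled at a running first look.** Seven weeks is 49 / 30.44 = 1.61 months. With even accrual of r per month, the number enrolled when the 6th patient finishes is 6 + 1.61r.
- r = 7.08: 6 + 11.4 = 17.4 enrolled, about 23 of 40 not yet enrolled.
- r = 10 (assumed): 6 + 16.1 = 22.1 enrolled, about 18 not yet enrolled.
- r = 25: 6 + 40.3 exceeds 40, so none are left.

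The documents give no accrual rate. The first and last values come from the enrollment period of approximately 2 years (Section 3.2):
- 170 patients over 24 months is 7.08 per month. Allowing for sequential Phase 1b cohorts gives almost the same rate. The shortest path through Table 5 (levels 1, 2, 3, 6, 7, 9, 11 and 13, with level 13 expanded to 6) uses 27 patients and nine 28-day windows: 252 days, or 8.3 months. Then 24 − 8.3 − 1.6 (the wait before expansion) = 14.1 months for 100 Phase 2 patients, or 7.1 per month.
- If Phase 1b used 60 patients as ten levels of 3 + 3 (an assumption), 20 windows take 560 days, or 18.4 months. Then 24 − 18.4 − 1.6 = 4.0 months remain, or about 25 per month.

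If all 100 Phase 2 patients are enrolled within the 2 years, 7.1 per month is therefore about the slowest rate and 23 about the largest saving. If enrollment overran, more would be left: at an assumed 4 per month, 6 + 6.4 = 12.4 enrolled and about 28 left.

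**The case against.** The best defence is that the literal reading defeats the rule's own purpose and so cannot be what was meant. Counting the first 6 and first 9, pausing recruitment, and asking the SMC about continued enrollment make sense only for a running check. That is right about intent. It does not repair the text: the sentence sets a different time point, the enrolled-so-far reading does not settle when to look, and the expansion rule shows that the protocol can state such timing plainly.

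Four stronger readings are tempting, and the documents do not support them:
- *The cohort has no safety oversight.* The SMC monitors this period (Section 5.5.3.2) and the whole study (Section 10). Section 5.6.1 stops enrollment for named events, Table 7 pauses it for a treatment-related Grade 5 toxicity, and visits are weekly for the first 6 weeks (Section 3.1). All of these act in real time.
- *The counted event is undefined.* The DLT criteria can serve. What is left is a loose term with no stated length of delay.
- *Failing to say pooled or per dose is an error.* The rule speaks of one cohort, and Section 5.5.3.3 says per arm where that is meant, so context favours pooled. This is missing detail.
- *A running check would spare a known number of patients.* The number runs from about 23 down to none within the 2-year premise.

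**Conclusion.** The rule is wrong as written. A toxicity trigger meant to act early is tied to a time when it can no longer limit enrollment in its own cohort. This follows from the text and needs no accrual assumption. The benefit of correcting it does depend on accrual: about 23, 18 or no patients not yet enrolled when the 6th patient finishes 7 weeks, at about 7, 10 or 25 per month with even enrollment. Under fast accrual, a look that waits for 7-week completion would also come too late, so the rule must fire as soon as the count is reached.

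Severity is minor. Other safeguards apply in real time, and Phase 2 never opened (SAP Section 4.8), so no patient was affected. The defect matters if Phase 2 is reopened or the section is reused.

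**What to change.** In Section 5.5.3.2, state that each trigger is evaluated when the 6th and the 9th treated patients have completed 7 weeks or discontinued, and immediately once 3 of the first 6 or 4 of the first 9 have had the event, without waiting for the rest of the cohort.

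As a secondary clarification, define the counted event as any Phase 2 DLT or a toxicity-related dose hold of more than 7 consecutive days, as in Phase 1b. Replacing postponement with DLT alone would not be neutral, because delays that meet no DLT criterion would stop counting.

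Also say whether the count is pooled or per dose group. Per-group counting looks at each dose separately but pauses more often. With two independent groups at the same rate, at least one pauses with probability 1 − (1 − t)², where t is the single-sequence total: 3.8%, 23.9% and 55.6% at event rates of 10%, 20% and 30%.

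The change is protocol wording and needs no extra patients. Its cost is a possible pause for SMC review, not a stop: 1.9%, 12.8% and 33.4% at the same rates for a single sequence. The 30% that Section 5.5.3.3 calls acceptable is a DLT rate. Counting holds as well can only raise the event rate, so pauses would be at least as frequent as for DLTs alone.
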